INFECTIONS AND INFESTATIONS			
	Skin infection 		Skin infection (Gr 2)
INVESTIGATIONS			
	Alanine aminotransferase increased		Alanine aminotransferase increased (Gr 3)
	Alkaline phosphatase increased		
	Aspartate aminotransferase increased		Aspartate aminotransferase increased (Gr 3)
	Blood bilirubin increased		Blood bilirubin increased (Gr 3)

CLOSE

Adverse Events with Possible Relationship to OSI-774 (erlotinib) (CTCAE 4.0 Term) [n= 3622]			Specific Protocol Exceptions to Expedited Reporting (SPEER)  (formerly known as ASael)
Likely (>20%)	Less Likely (<=20%)	Rare but Serious (<3%)	
METABOLISM AND NUTRITION DISORDERS			
Anorexia			Anorexia (Gr 3)
	Dehydration		Dehydration (Gr 3)
NERVOUS SYSTEM DISORDERS			
	Dysgeusia		Dysgeusia (Gr 2)
	Headache		Headache (Gr 2)
		Intracranial hemorrhage	
RESPIRATORY, THORACIC AND MEDIASTINAL DISORDERS			
	Cough		Cough (Gr 2)
	Dyspnea		Dyspnea (Gr 3)
	Epistaxis		
	Pneumonitis		Pneumonitis (Gr 3)
SKIN AND SUBCUTANEOUS TISSUE DISORDERS			
	Alopecia		Alopecia (Gr 2)
	Dry skin		Dry skin (Gr 2)
		Erythema multiforme	
	Nail loss		Nail loss (Gr 2)
		Palmar-plantar erythrodysesthesia syndrome	
	Pruritus		Pruritus (Gr 2)
	Rash acneiform		Rash acneiform (Gr 2)
Rash maculo-papular			Rash maculo-papular (Gr 3)

 This table will be updated as the toxicity profile of the agent is revised. Updates will be distributed to all Principal Investigators at the time of revision. The current version can be obtained by contacting [contact]. Your name, the name of the investigator, the protocol and the agent should be included in the e-mail.

 Gastrointestinal hemorrhage includes Anal hemorrhage, Cecal hemorrhage, Colonic hemorrhage, Duodenal hemorrhage, Esophageal hemorrhage, Esophageal varices hemorrhage, Gastric hemorrhage, Hemorrhoidal hemorrhage, Ileal hemorrhage, Intra-abdominal hemorrhage, Jejunal hemorrhage, Lower gastrointestinal hemorrhage, Oral hemorrhage, Pancreatic hemorrhage, Rectal hemorrhage, Retroperitoneal hemorrhage, and Upper gastrointestinal hemorrhage under the GASTROINTESTINAL DISORDERS SOC.

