**Warning:** Treatment with erlotinib should be used with extra caution in patients with total bilirubin > 3 x ULN. Patients with hepatic impairment (total bilirubin > ULN or Child-Pugh A, B and C) should be closely monitored during therapy with erlotinib. Erlotinib dosing should be interrupted or discontinued if changes in liver function are severe such as doubling of total bilirubin and/or tripling of transaminases in the setting of pretreatment values outside normal range.

**Warning:** Cases of hepatic failure and hepatorenal syndrome (including fatalities) have been reported during use of erlotinib, particularly in patients with baseline hepatic impairment. Therefore, periodic liver function testing (transaminases, bilirubin, and alkaline phosphatase) is recommended. In the setting of worsening liver function tests, dose interruption and/or dose

reduction with frequent liver function test monitoring should be considered. Erlotinib dosing should be interrupted or discontinued if total bilirubin is  $> 3 \times \text{ULN}$  and/or transaminases are  $> 5 \times \text{ULN}$  in the setting of normal pretreatment values.

**Warning:** Cases of hepatorenal syndrome, acute renal failure (including fatalities), and renal insufficiency have been reported. Some were secondary to baseline hepatic impairment while others were associated with severe dehydration due to diarrhea, vomiting, and/or anorexia or concurrent chemotherapy use. In the event of dehydration, particularly in patients with contributing risk factors for renal failure (e.g., pre-existing renal disease, medical conditions or medications that may lead to renal disease, or other predisposing conditions including advanced age), erlotinib therapy should be interrupted and appropriate measures should be taken to intensively rehydrate the patient. Periodic monitoring of renal function and serum electrolytes is recommended in patients at risk of dehydration.

**Gastrointestinal Perforation:** Patients receiving erlotinib are at increased risk of developing gastrointestinal perforation, which was observed uncommonly. Some cases had a fatal outcome. Patients receiving concomitant anti-angiogenic agents, corticosteroids, NSAIDs, and/or taxane based chemotherapy, or who have prior history of peptic ulceration or diverticular disease, are at increased risk. Erlotinib should be permanently discontinued in patients who develop gastrointestinal perforation.

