5.3 Clinical/Laboratory Criteria

- \_\_\_\_\_ a. Patients must have a complete physical examination and medical history within 28 days prior to registration.
- \_\_\_\_\_ b. Patients must have a Zubrod performance status of 0 - 2 (see [Section 10.4](#)).
- \_\_\_\_\_ c. Patients must have adequate hematologic function as documented by a WBC  $\geq$  2,000/mcL, an ANC  $\geq$  1,000/mcL, and a platelet count  $\geq$  75,000/mcL. These tests must be obtained within 14 days prior to registration.
- \_\_\_\_\_ d. Patients must have adequate hepatic function as evidenced by serum bilirubin  $\leq$  1.5 x institutional upper limits of normal (ULN). Serum transaminase (SGOT/AST and SGPT/ALT) must be  $\leq$  1.5 x the institutional ULN unless the liver is involved with the tumor, in which case serum transaminase (SGOT/SGPT) must be  $\leq$  5 x the institutional ULN. These tests must be obtained within 14 days prior to registration.
- \_\_\_\_\_ e. Serum creatinine must be  $\leq$  2 x the institutional ULN and obtained within 14 days prior to registration.
- \_\_\_\_\_ f. Sodium, potassium and calcium must be obtained within 14 days prior to registration.
- \_\_\_\_\_ g. Patients with a known history of the following corneal diseases are not eligible: dry eye syndrome, Sjogren's syndrome, keratoconjunctivitis sicca, exposure keratopathy, Fuch's dystrophy or other active disorders of cornea.
- \_\_\_\_\_ h. Patients known to be HIV-positive and receiving combination anti-retroviral therapy are not eligible due to possible pharmacokinetic interactions with erlotinib and ARQ 197.
- \_\_\_\_\_ i. Patients must be able to take oral medications. Patients must not have gastrointestinal tract disease resulting in an inability to take oral medication or a requirement for IV alimentation, prior surgical procedures affecting absorption, or active peptic ulcer disease. Patients with intractable nausea or vomiting are not eligible.

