8.6 Erlotinib Dose Modificationa

Toxicity (NCI CTCAE v4.0)	Dose Modification
Diarrhea	
Grade 1	None. Initiate therapy with loperamide.(8.7a)
Grade 2	Hold erlotinib. Initiate loperamide until resolution to Grade 0-1. Resume therapy at the same dose.
Grade 3 b or 4 b	Hold erlotinib. Initiate therapy with loperamide and appropriate supportive care until resolution to Grade 0 or 1 and then restart at 1 dose level lower
Rash	
Grade 1	None
Grade 2	None. Initiate treatment (8.7b) . If rash persists and is intolerable or worsens over 10 – 14 days, then reduce by 1 dose level.
Grade 3	Reduce by 1 dose level. If rash persists or worsens over 10 – 14 days, then interrupt erlotinib until resolution to Grade 0, 1 or 2 and then restart 1 dose level lower.
Grade 4	Permanently discontinue erlotinib.
Interstitial Lung Disease	
Any Grade	If ILD is suspected, erlotinib should be interrupted immediately pending diagnostic evaluation. If ILD is diagnosed, erlotinib should be discontinued permanently and appropriate treatment instituted as necessary.
Other Toxicities Attributable to Erlotinib	
Grade 1 or 2	None
Grade 3 or 4 b, c	Interrupt erlotinib until resolution to Grade 0 or 1 and then restart 1 dose level lower.
Other Toxicities (hematologic and non-hematologic) attributable to ARQ 197	
Grade 1 or 2	None
Grade 3 or 4	Hold erlotinib until ARQ 197 is resumed. If toxicity was deemed related to ARQ 197 no dose reduction of erlotinib is indicated

- (a) Doses that have been reduced should not be re-escalated. Any patient who fails to tolerate treatment at 50 mg/day will discontinue erlotinib and continue on single agent ARQ 197.
- (b) If the event does not resolve to Grade 0 or 1 within 21 days, erlotinib will be discontinued and patient will continue on a single agent ARQ 197
- (c) Only if  $\geq 2$  Grade level change from baseline

Erlotinib Dose Level Reductions

Starting Dose	First Reduction	Second Reduction
150 mg/day	100 mg/day	50 mg/day

NOTE: Any patient who fails to tolerate erlotinib at 50 mg/day will continue on single agent ARQ 197. If a treatment is delayed more than 21 days for the resolution of erlotinib-related toxicities to Grade 0 or 1, discontinue erlotinib and continue ARQ 197 alone.

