## 8.7 Suggested management of toxicities

- a. Diarrhea. The recommended dose of loperamide is 4 mg at first onset, followed by 2 mg every 2 to 4 hours until diarrhea resolves for 12 hours. In the event of severe or persistent diarrhea, nausea, anorexia, or vomiting associated with dehydration, erlotinib therapy should be interrupted and appropriate measures should be taken to intensively treat the dehydration. Since there have been rare reports of hypokalemia and/or acute renal failure (including fatalities), secondary to severe dehydration, renal function and serum electrolytes (including potassium) should be monitored in this setting.
- b. Rash/skin toxicity. Patients should be informed that skin toxicity is to be expected during treatment with erlotinib. Skin toxicity may take the form of dry skin, rash, acneiform eruption, or hair or nail changes. Prophylactic treatment of the skin may prevent or reduce skin toxicity. The patient should be encouraged to use an alcohol-free, emollient cream applied twice a day to the entire body as soon as the patient starts therapy with erlotinib. Creams and ointments are recommended because they have a greater ability to retain moisture than lotions. Examples of suitable emollient creams include: Neutrogena® Norwegian formula, SARNA® Ultra, Vanicream™, Aveeno® (fragrance-free formulation), and Eucerin® cream. Other over-the-counter aqueous creams or emulsifying ointments may also provide symptomatic benefit. Lotions should be avoided because they often contain alcohol, which will dry the skin. Patients should also be encouraged to use a titanium dioxide or zinc oxide-based sunscreen product applied to sun-exposed areas twice per day.

Patients who develop skin toxicity and are symptomatic should be treated with topical therapy such as hydrocortisone cream or clindamycin gel. If needed, oral minocycline or oral doxycycline may be combined with the topical therapy. A topical immunomodulating cream such as Elidel could also be considered. For more severe rash, oral corticosteroids may be beneficial. Patients who fail to respond to these measures may have the dose of erlotinib interrupted or reduced.

Minocycline is known to interfere with anticoagulants and oral contraceptives. Patients treated with minocycline who are taking anticoagulants and/or oral contraceptives should be monitored accordingly.

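### For Grade 1–2 dehydration attributed to erlotinib without Grade 2 or higher diarrhea, Section 3.2b interrupts the drug, Section 8.6 leaves the dose unchanged, and nothing says which governs

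*Combined protocol and SAP*

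**What the plan says.** Three places in the protocol bear on dehydration in a patient taking erlotinib.

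- **Section 3.2b** (erlotinib toxicology, warning on hepatorenal syndrome and acute renal failure): "In the event of dehydration, particularly in patients with contributing risk factors for renal failure", the instruction is that "erlotinib therapy should be interrupted and appropriate measures should be taken to intensively rehydrate the patient". No grade is given. Renal risk factors are stressed, but the sentence is not confined to patients who have them.
- **Section 8.7a** (suggested management, diarrhea): "In the event of severe or persistent diarrhea, nausea, anorexia, or vomiting associated with dehydration, erlotinib therapy should be interrupted". Here the severity or persistence condition is attached to the gastrointestinal symptom; the dehydration itself is not graded.
- **Section 8.6** (erlotinib dose modification table): rows exist for diarrhea, rash and interstitial lung disease, and there are residual rows, but none for dehydration. Dehydration is a listed erlotinib event in the Section 3.2b adverse-event table, so when attributed to erlotinib it belongs to "Other Toxicities Attributable to Erlotinib". That row reads "Grade 1 or 2 None" for the lower grades. For Grade 3 or 4 it reads "Interrupt erlotinib until resolution to Grade 0 or 1 and then restart 1 dose level lower", limited by footnote (c) to a change of at least two grades from baseline.

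Section 8.6 refers to Section 8.7a once, from its Grade 1 diarrhea row. The residual row refers neither to 8.7a nor to 3.2b.

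**The concern.** A site treating an Arm 2 patient with mild or moderate dehydration finds one instruction in the drug information and the opposite one in the dose table. The protocol itself ties dehydration on erlotinib to acute renal failure, with fatalities, and names pre-existing renal disease among the contributing factors. The trial enrolls patients with renal cell carcinoma, and under Section 5.3e "Serum creatinine must be" no more than twice the institutional upper limit of normal, so some patients may enter with reduced renal function.

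There is a smaller consequence for the data. Section 11.3 will summarise, by arm, how often and how far dose modifications were required. For this event, what counts as required depends on the section read. If sites read differently, the Arm 2 summary mixes drug tolerability with differences in interpretation.

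**Working it through.** The plan states no figure to reproduce on this point, so the check is a comparison of the rules, followed by one bound.

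**Step 1. What each section directs, by case (dehydration attributed to erlotinib).**

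| Case | 3.2b | 8.7a | 8.6 | Result |
|---|---|---|---|---|
| A. Grade 1–2, no severe or persistent GI symptom | Interrupt | Not triggered | No change | 3.2b and 8.6 conflict |
| B. Grade 1–2, with persistent Grade 1–2 nausea, vomiting or anorexia, or persistent Grade 1 diarrhea | Interrupt | Interrupt | No change | 3.2b and 8.7a conflict with 8.6 |
| C. Grade 1–2, with Grade 2 or higher diarrhea | Interrupt | Interrupt if the symptom is severe or persistent | Hold, through the diarrhea row | Agree on interruption |
| D. Grade 3–4, at least two grades above baseline | Interrupt | Interrupt if triggered | Interrupt, restart one level lower | Agree on interruption |
| E. Grade 3–4, less than two grades above baseline | Interrupt | Interrupt if triggered | Footnote (c) removes the action | Differ |

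The conflict that matters is in A and B. It also disappears where another event already holds erlotinib: a Grade 3–4 erlotinib toxicity that meets footnote (c), or a hold of ARQ 197, which under Section 8.5 holds erlotinib too. Attributing the dehydration to ARQ 197 instead does not help, because that row of 8.6 also gives no change at Grade 1 or 2.

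Case E needs baseline dehydration of Grade 2 or worse for a Grade 3 event (3 − 2 = 1, below 2), or of Grade 3 for a Grade 4 event (4 − 3 = 1). It should be very rare and is not part of the point.

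**Step 2. Does any rule rank the sections?** Section 8.2b takes the greatest reduction when several toxicities occur with one agent. It does not address two instructions for a single toxicity, and 3.2b orders an interruption without stating a reduction. No other text gives 3.2b, 8.6 or 8.7a precedence.

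**Step 3. Restart after a Grade 1–2 interruption.** Sections 3.2b and 8.7a give no restart dose. Section 8.6 gives none either, because it does not interrupt for these cases. Its usual condition for resuming, resolution to Grade 0 or 1, is already met by Grade 1 dehydration, so it cannot say when to resume. The nearest rows differ: Grade 2 diarrhea resumes at the same dose, while a Grade 3–4 residual toxicity resumes one level lower. Because re-escalation is barred (Section 8.2d and footnote (a) of 8.6), a reduction borrowed from the latter row would be permanent.

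**Step 4. Size.** The erlotinib adverse-event list, based on 3,622 patients, puts dehydration in its at-most-20% column.

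- Full Arm 2 accrual: 0.20 × 35 = 7 patients.
- Arm 2 stopped at stage one: 0.20 × 20 = 4 patients.

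These are ceilings over all grades. The number in cases A and B is smaller by an unknown amount, since the documents give neither a grade distribution nor the overlap with Grade 2 or higher diarrhea.

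**The case against.** The best defence is that Section 8.6 governs. Section 3.2b is drug information, its instruction follows a sentence about severe dehydration and calls for intensive rehydration, and Section 8.7 is headed as suggestions. On that reading 3.2b concerns severe cases only. The reading is reasonable, but the instruction itself carries no severity condition and no text subordinates 3.2b or 8.7a to 8.6. The heading of 8.7 also does not settle the matter, because the Grade 1 diarrhea row of 8.6 sends the site to 8.7a, which interrupts for persistent diarrhea with dehydration although that row makes no dose change. Section 7.0 offers a contact for dose questions, which can resolve individual cases but does not make sites consistent.

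Other parts of the defence stand and set the limits of the point. A reader might infer that every Grade 1–2 dehydration event is caught. It is not: Grade 2 or higher diarrhea already leads to a hold under 8.6, and Section 3.2b names diarrhea as a source of dehydration on this drug. A reader might also count three mutually incompatible triggers, but 8.7a is a narrower instance of 3.2b with the same action, and those two can be followed together. Nor do the restart doses conflict; for Grade 1–2 interruptions the documents are silent.

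**Conclusion.** The point holds within those limits. For Grade 1–2 dehydration attributed to erlotinib, without Grade 2 or higher diarrhea or another event that already holds the drug, Section 3.2b interrupts and the residual row of Section 8.6 does not, and the protocol does not say which to follow. The missing restart dose is a separate gap.

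The number of patients affected cannot be estimated. It would be tempting to report 7 affected patients, but that is the top of a frequency category, covers all grades, and assumes both full accrual and that the pooled erlotinib frequency carries over to the combination arm.

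The consequence is for patient safety and for the descriptive dose-modification summary in Section 11.3. The documents do not support a claim that the two-stage design is affected: its response thresholds, significance level and power do not depend on this rule. The conclusion rests on reading 3.2b as written, without importing the word severe from the preceding sentence. It takes no view on which instruction is clinically right.

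**What to change.** Reconcile Sections 3.2b, 8.6 and 8.7a. Either add a dehydration row to the Section 8.6 table, or state which passage governs when 3.2b or 8.7a gives an event-specific instruction that differs from the residual row. In both cases state the trigger, the condition for resuming and the restart dose, all chosen by the study team, and align the wording of the other two sections.

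The cost is one table row or one cross-reference in a protocol amendment, with no added patients, visits, tests or analyses. The protocol is marked closed in May 2014 and was still being revised in 2016. If no patient remains on erlotinib, the useful step is a sentence beside the Section 11.3 dose-modification summary saying that sites had differing instructions for low-grade dehydration.

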#### 4.0 STAGING CRITERIA

This section is not applicable to this study.

## 5.0 ELIGIBILITY CRITERIA

Each of the criteria in the following section must be met in order for a patient to be considered eligible for registration. Use the spaces provided to confirm a patient's eligibility. For each criterion requiring test results and dates, please record this information on the **S1107** Prestudy Form and submit via MediData Rave® (see [Section 14.0](#)). Any potential eligibility issues should be addressed to the Data Operations Center in Seattle at [name] prior to registration.

In calculating days of tests and measurements, the day a test or measurement is done is considered Day 0. Therefore, if a test is done on a Monday, the Monday 2 weeks later would be considered Day 14. This allows for efficient patient scheduling without exceeding the guidelines. If Day 14, 21, 28, 42 or 56 falls on a weekend or holiday, the limit may be extended to the next working day.

**SWOG Patient No.** \_\_\_\_\_

**Patient's Initial (L,F,M).** \_\_\_\_\_

### 5.1 Disease Related Criteria

- \_\_\_\_\_ a. Patients must have histologically or cytologically confirmed papillary histology renal cell carcinoma which is metastatic, or locally advanced and unresectable. Mixed histologies will be allowed provided that they contain  $\geq 50\%$  of the papillary component.
- \_\_\_\_\_ b. Patients must have measurable disease, defined as at least one lesion that can be accurately measured in at least one dimension (see [Section 10.0](#)). X-rays, scans or physical examinations used for tumor measurement must have been completed within 28 days prior to registration. X-rays, scans or physical examinations for non-measurable disease must have been completed within 42 days prior to registration. All disease must be assessed and documented on the Baseline Tumor Assessment Form.
- \_\_\_\_\_ c. Patients with metastatic disease who have a resectable primary tumor and are deemed a surgical candidate may have undergone resection. At least 28 days must have elapsed since surgery and patient must have recovered from any adverse effects of surgery.
- \_\_\_\_\_ d. Patients with a history of brain metastases who are asymptomatic and have not received steroid therapy in the 14 days prior to registration are eligible. Anti-seizure medications are allowed provided they are non-enzyme inducing (e.g. topiramate, levatiracetam, gabapentin).

### 5.2 Prior Therapy Criteria

- \_\_\_\_\_ a. Patients may have received up to one prior systemic therapy for advanced or metastatic renal cell carcinoma. Patients must not have received a MET inhibitor or erlotinib as prior therapy. At least 21 days must have elapsed since completion of prior systemic therapy, 42 days for nitrosoureas or mitomycin C. Patients must have recovered from all associated toxicities at the time of registration.
- \_\_\_\_\_ b. Patients may have received prior radiation therapy, but must have measurable disease outside the radiation port. At least 21 days must have elapsed since completion of prior radiation therapy. Patients must have recovered from all associated toxicities at the time of registration.
- \_\_\_\_\_ c. Patients must not be receiving or planning to receive any other investigational agents.

SWOG Patient No. \_\_\_\_\_

Patient's Initial (L,F,M). \_\_\_\_\_

5.3 Clinical/Laboratory Criteria

- \_\_\_\_\_ a. Patients must have a complete physical examination and medical history within 28 days prior to registration.
- \_\_\_\_\_ b. Patients must have a Zubrod performance status of 0 - 2 (see [Section 10.4](#)).
- \_\_\_\_\_ c. Patients must have adequate hematologic function as documented by a WBC  $\geq$  2,000/mcL, an ANC  $\geq$  1,000/mcL, and a platelet count  $\geq$  75,000/mcL. These tests must be obtained within 14 days prior to registration.
- \_\_\_\_\_ d. Patients must have adequate hepatic function as evidenced by serum bilirubin  $\leq$  1.5 x institutional upper limits of normal (ULN). Serum transaminase (SGOT/AST and SGPT/ALT) must be  $\leq$  1.5 x the institutional ULN unless the liver is involved with the tumor, in which case serum transaminase (SGOT/SGPT) must be  $\leq$  5 x the institutional ULN. These tests must be obtained within 14 days prior to registration.
- \_\_\_\_\_ e. Serum creatinine must be  $\leq$  2 x the institutional ULN and obtained within 14 days prior to registration.
- \_\_\_\_\_ f. Sodium, potassium and calcium must be obtained within 14 days prior to registration.
- \_\_\_\_\_ g. Patients with a known history of the following corneal diseases are not eligible: dry eye syndrome, Sjogren's syndrome, keratoconjunctivitis sicca, exposure keratopathy, Fuch's dystrophy or other active disorders of cornea.
- \_\_\_\_\_ h. Patients known to be HIV-positive and receiving combination anti-retroviral therapy are not eligible due to possible pharmacokinetic interactions with erlotinib and ARQ 197.
- \_\_\_\_\_ i. Patients must be able to take oral medications. Patients must not have gastrointestinal tract disease resulting in an inability to take oral medication or a requirement for IV alimentation, prior surgical procedures affecting absorption, or active peptic ulcer disease. Patients with intractable nausea or vomiting are not eligible.
- \_\_\_\_\_ j. Patients must not be pregnant or nursing because ARQ 197 and erlotinib have the potential for teratogenic or abortifacient effects. There is an unknown but potential risk for adverse events in nursing infants secondary to treatment of the mother with ARQ 197 or erlotinib. Women/men of reproductive potential must have agreed to use an effective contraceptive method. A woman is considered to be of "reproductive potential" if she has had menses at any time in the preceding 12 consecutive months. In addition to routine contraceptive methods, "effective contraception" also includes heterosexual celibacy and surgery intended to prevent pregnancy (or with a side-effect of pregnancy prevention) defined as a hysterectomy, bilateral oophorectomy or bilateral tubal ligation. However, if at any point a previously celibate patient chooses to become heterosexually active during the time period for use of contraceptive measures outlined in the protocol, he/she is responsible for beginning contraceptive measures.

CLOSED PERIODIC 05/17/2014

**SWOG Patient No.** \_\_\_\_\_

**Patient's Initial (L,F,M).** \_\_\_\_\_

